**Title of Project**

**Tandem DBS for Parkinson's Disease: A Pilot Study Utilizing STN/GPi + hypothalamic stimulation**

**DESCRIPTION**

With progression of symptoms, patients with Parkinson's disease (PD) frequently develop significant disability despite optimal medical therapy. Surgical treatments, such as subthalamic or globus pallidal-deep brain stimulation (DBS), offer some benefit for selected patients. However, a large percentage of patients subsequently develop dementia.

Preliminary studies have identified stimulation of the hypothalamus/fornix as potentially useful in improving cognitive functioning acutely and there are theoretical reasons why such stimulation may lead to neurogenesis and potentially obviate future cognitive decline/dementia.

We propose a pilot study of dual hemispheric stimulation of the subthalamic nucleus (STN) and fornix/hypothalamus in 12 PD patients experiencing motor disability despite optimal medical therapy, who would otherwise be undergoing STN-DBS. These individuals may also have mild cognitive impairment. The study will include measures of motor and cognitive function.

## **Background**

### Tandem Deep Brain Stimulation for Parkinson's Disease

#### Abstract

Deep brain stimulation (DBS) targets for Parkinson's disease have been limited to neuronal regions wherein lesions have produced beneficial effects. Improvements in imaging allow placement in small and novel targets. Additionally, due to the ability of impulse generators to accommodate multiple electrodes, simultaneous stimulation in multiple neuronal regions is possible.

Given that the two most disabling clinical features of Parkinson's disease, namely postural instability and dementia, have evaded effective treatment, consideration for new structural targets is warranted. Characteristics of dementia in parkinsonism include progressive deficits in attention and executive function. Additionally, many patients experience pronounced variability in cognition with profound fluctuations/variability in attention and alertness.

Anecdotal and initial trial reports concerning DBS to the fornix/hypothalamus have been associated with improvement in memory function and reductions in expected cognitive decline in patients with early Alzheimer's disease. The fornix constitutes the major inflow and output pathway from the hippocampus and medial temporal lobe.

I hypothesize that tandem DBS, targeting the STN/GPi and fornix/hypothalamus and/or hippocampus may have a positive impact on improving cognitive function and/or reducing risk for subsequent dementia with Lewy bodies/Parkinson dementia. Such targets also pose potential negative ramifications. Nevertheless, given the tremendous disability produced by dementia, new structural targets require systematic study.

### Tandem Deep Brain Stimulation for Parkinson's Disease

Deep brain stimulation (DBS) targets for Parkinson's disease (PD) have been limited to neuronal regions wherein lesions have produced beneficial effects. Every DBS target routinely employed at international centers: ventral intermediate nucleus of the thalamus, subthalamic nucleus, or globus pallidus internus, have been historically lesioned with documentation of ensuing motor benefit. The positive ramifications have included predominantly improvement in motor function and functional "on" time. Patients undergoing surgery have been highly selected; PD patients with depression and dementia have consistently been avoided as surgical candidates [1].

While most series of DBS surgery for PD patients find minimal changes in cognition within the first year following surgery, longitudinal series subsequently document that cognitive decline and dementia are still commonplace. Additionally, most DBS series have avoided operating on elderly PD patients who are at most risk for dementia. We

have suggested for some time that unilateral STN-DBS be routinely employed (as opposed to immediate bilateral surgery) in PD, as it may be therapeutically effective and carry fewer cognitive complications, particularly in elderly patients [2].

Most long-term follow-up indicate that speech, axial motor features and cognitive decline frequently become apparent in PD patients receiving DBS [3]. Studies examining specific cognitive outcomes more than two years after surgery indicate that the majority of STN-DBS patients demonstrate significant declines in nonverbal memory, semantic fluency, and processing speed, with the same percentage converting to dementia as those PD who were not surgical patients [4]. Hence, there is no evidence to suggest that current DBS targets, even employed in a selected, non-demented, non-depressed cohort, subsequently minimize the risk for future dementia.

In summary, currently available pharmacological and surgical therapies do not consistently, effectively ameliorate balance and cognitive decline/dementia or reduce their risk, and frequently exacerbate these problems in the short-term.

#### Dementia and Parkinson's disease

Dementia in Parkinson's disease (PD) represents the most frequent, eventually disabling feature of this common neurodegenerative disorder. It also is a strong predictor of survival [5].

Parkinson dementia/dementia with Lewy bodies represents the second most common form of disabling dementia. Characteristics of dementia in parkinsonism include progressive dementia with deficits in attention and executive function [6]. Recurrent, complex visual hallucinations frequently occur and may be accompanied by REM sleep behavior disorder (concurrently or prior to development of other features). Additionally, many patients experience pronounced variability in cognition with profound fluctuations/variability in attention and alertness. Fluctuations in cognitive functioning and deficits in attention and executive function, often without prominent memory impairment, is a core feature of dementia with Lewy bodies [6], and occurs particularly in early stages. Such variability is a hallmark of dementia with Lewy bodies that differentiates this form of cognitive decline from Alzheimer's disease and aging [7].

Unfortunately, the two most common disabling clinical features of PD, namely postural instability leading to falls and dementia have evaded effective treatment. Additionally, these features are increasingly common in aging PD patients, precisely the demographic who are avoided by most centers performing DBS surgery.

#### Could DBS potentially impact cognitive decline/dementia in PD?

DBS with high-frequency stimulation of the limbic circuitry, namely the anterior thalamic nuclei, demonstrates neurogenesis of neurons in the dentate gyrus of the hippocampus, a component of the limbic circuit.

The ability to produce adult hippocampal neurogenesis has also been associated with effective antidepressant treatments. Studies in mice have demonstrated that stimulation of the ATN may produce increases in neural progenitors in the dentate gyrus of the same variety that can be stimulated by fluoxetine and physical exercise [8]. This suggests that ATN stimulation might be useful for limbic circuitry activation and influence on cognition and mood. While most clinical studies in PD patients do not suggest that cognition is negatively impacted by DBS per se, this may also be possible. DBS of the anterior thalamus at high current has shown the ability to impair memory in rat animal models [9].

An anecdotal report concerning DBS in the fornix and hypothalamus in a patient being treated for obesity included descriptions of impressive memory enhancement [10]. While on the operating table, this patient was able to provide detailed memory recollections from 30 years previous. Subsequent evaluation disclosed that there were EEG effects in the hippocampal formation and medial temporal lobe in conjunction with high-intensity stimulation (3-5 V, 60-microsecond pw, 130 Hz). Additionally, performance on neuropsychological testing after chronic hypothalamic stimulation demonstrated improvements in attention, verbal learning (short- and long-delay recall) and spatial associative learning. This testing suggested that hypothalamic stimulation induced enhanced recollection in the memory process. The mechanism thought to be responsible was driving activity of the hippocampal memory circuit through stimulation of the fornix. The fornix represents the major axonal bundle from the hippocampus and medial temporal lobe. Lesions in the fornix are also well known to produce memory deficits in humans. In contrast in this instance, apparent driving of activity in the ipsilateral medial temporal lobe to unilateral hypothalamic stimulation (“on” state), was associated with increased memory ability.

A subsequent trial has ensued examining the impact of DBS on memory circuits in Alzheimer’s disease (AD) [11]. This trial recruited six patients with early AD. All had Clinical Dementia Rating scores of 0.5 or 1.0 [12] and scores between 15-26 on the Mini Mental State Examination (MMSE)[13]. Each were implanted bilaterally in the vertical portion of the fornix within the hypothalamus. Assessments with the Alzheimer’s Disease Assessment Scale, Cognitive Subscale (ADAS-Cog)[14] took place at baseline and 6 and 12-months post-operatively. After 6 months of stimulation, 4 of 6 patients showed improvement, with lowering of 1.3-4.0 points in the ADAS-Cog scores. This magnitude compares favorably to the reported impact of donepezil in mild cognitive impairment, which is 0.5 points [15].

After 12 months, one patient had 4.4 points lower than baseline, 2 patients a 2-point increase, 1 patient a 5-point increase, and 2 patients >5 point increases. The expected change in the cohort of 6 was: 2 patients had less than expected increases, 1 more, and 3 within the expected range. Interestingly the patient with the greatest improvement experienced the most vivid experiential experience with stimulation during surgery, as had been the case with the original anectodal patient reported. Functional imaging carried out in this trial also suggested that fornix/hypothalamic-DBS produced changes in the

cognitive and limbic brain areas (improved glucose metabolism), were the basis for observed changes in some of the AD patients. These authors also suggest that DBS may drive greater delivery of neurotrophin brain-derived neurotrophic factor and influence neurogenesis in the diseased hippocampus.

#### Hypothesis: Tandem DBS for PD

Given that 1) the most disabling and common negative consequence of PD is dementia for which there is no means to avoid or beneficial treatment, and 2) there is some evidence that DBS can potentially safely impact upon memory, I suggest that tandem DBS, namely targeting both STN (or GPi) and the fornix/hypothalamus and/or hippocampus may improve both motor and cognitive function (immediate and future). As such, tandem DBS with STN/GPi + fornix/hypothalamus for PD patients should be considered for systematic study.

DBS of the fornix/hypothalamus and/or hippocampus may have a positive impact on cognitive function and/or reducing risk for subsequent dementia with Lewy bodies/Parkinson dementia.

Potential studies could include PD patients with:

- normal cognition
- mild cognitive impairment
- mild dementia

Studies with patients who have normal cognition could determine if DBS of the fornix/hypothalamus had any impact on the natural course of the disorder and likelihood of subsequent development of dementia. Studies engaging patients with cognitive dysfunction could test whether DBS of the fornix/hypothalamus was capable of providing symptomatic improvement through improved alertness, attention, memory and other performance metrics.

#### Logistical Possibilities

Originally, impulse generators for deep brain stimulation electrodes accommodated only single quadric-polar brain electrodes. Consequently, deep brain stimulation was necessarily constrained by the lack of pulse generator flexibility. Currently available impulse generators readily accept multiple brain electrodes. Therefore, it is logically possible to consider utilizing multiple brain electrodes simultaneously. The studies suggested would require at least two electrodes to be placed in one cerebral hemisphere (one for motor improvement and one for potential cognitive implications). Trials would need to include designs to determine the impact of DBS in targets considered singly (e.g. STN or fornix/hypothalamus) and in combination (e.g. STN and fornix/hypothalamus).

I propose controlled studies implanting PD patients who are otherwise undergoing unilateral DBS-GPi or DBS-STN with a unilateral DBS electrode with stimulation to the

fornix/hypothalamus region, i.e. tandem DBS. Such patients would receive a single IPG, as would otherwise be required for such surgery. Patients subsequently undergoing second-sided surgery for motor parkinsonism would concurrently also receive a second electrode with stimulation for the fornix/hypothalamus. Stimulation to the fornix/hypothalamus would be accomplished with either the same rate/frequency as for the unilateral basal ganglia structure or utilize 3.0-3.5 V with a frequency of 130 Hz and pulse width of 90 microseconds.

Neuropsychological studies and dementia status immediately prior to and years post-operatively would form the primary outcome measure for these tandem DBS studies. Historical results, with single hemispheric electrodes (either unilateral or bilateral) could serve as potential comparative data for secondary analyses.

MRI scans will be completed for serial hippocampal volume measures. Scans will be evaluated by [name].

Pathological studies of brain from patients at death would subsequently help to determine the nature of results, including ability to ascertain whether neurogenesis or other mechanism might be associated with fornix/hypothalamus-DBS/tandem DBS.

### Summary

DBS utilizing “traditional motor targets” for PD patients has provided improvement in functional “on” time and reduced tremor compared to standard medical therapy. However, subsequent risk for cognitive decline/dementia remains and development of these features leads to early disability and death. Potential improvements in cognitive function and neurogenesis are conceivable with tandem DBS targeting STN/GPi and the fornix/hypothalamus and should now be considered for systematic study in PD.

#### Acknowledgments

[name] is partially supported by the NIH/NINDS P50-NS072187 and NIH/NINDS NS057567, research funding from Advanced Neuromodulation Systems, Inc./St. Jude Medical, and a gift from [name], and [name] (MCF #90052031/PAU #90052).

## RESEARCH DESIGN AND METHODS

### Experimental Subjects

#### Inclusion/Exclusion Criteria

All patients will be enrolled from the practice of the primary investigator. It is anticipated that PD patients eligible for this study will range from 40-80 years and will have been symptomatic with parkinsonism for 7-20 years.

The study will include PD patients in whom optimal medical therapy has failed to relieve the patient from significant disability owing to parkinsonism. PD will be diagnosed by the principal investigator on the basis of the presence of at least 2 of 3 cardinal features of parkinsonism (resting tremor, rigidity, and bradykinesia) without known cause. Patients with prominent and early dysautonomia or ataxia or downgaze palsy or pyramidal signs will be excluded. Response to levodopa should be specified as more than minimal (reductions in UPDRS motor scoring of 20% or greater when “off” scores are compared to “on” scores during the drug motor response profile) and as sustained (e.g. for at least five years).

All patients will have responsiveness to levodopa (as defined by UPDRS changes above). Common causes for significant disability will be intractable tremor, levodopa-induced dyskinesias and other motor fluctuations. Optimal medical therapy will consist of appropriate use of levodopa and at least one dopamine agonist under the direction of the principal investigator. Common causes for significant disability will be motor fluctuations, levodopa-induced dyskinesias, intractable tremor, other motor disability including gait disturbances. Individuals with normal or mild cognitive impairment as a diagnosis following neuropsychological study will be eligible for the study.

Exclusionary criteria will include clinically significant dementia (MMSE  $\leq 23$ ), Hoehn & Yahr [Hoehn, 1967 #1839] stage I or V disease, other significant neurological or psychiatric disease, previous pallidotomy or thalamotomy, previous placement of other implantable devices, and secondary parkinsonism (non-idiopathic parkinsonism). Patients with the aforementioned characteristics (without exclusionary criterion) are defined as surgical candidates.

The study will seek to include women and members of minority groups.

The principal investigator will discuss the study with surgical candidates. Patients will not incur any financial charges or responsibility relating to this study. Consent for participation in this study will be sought and obtained by the primary investigator and study coordinator. The information provided to prospective subjects will include the details regarding each surgical procedure and the risks inherent with surgery (as listed below) will be that included on the IRB-approved consent form with consent being documented by written or econsent signature of the patient.

Potential risks for participation in this study include death, stroke, hemiparesis, and visual field deficits, and all other risks related to stereotactic brain surgery. The likelihood of such occurrences is generally reported to be approximately 2%. At our institution there have been no such serious adverse events in the >100 procedures performed during the past 2 years. Should patients expect greater improvement than obtained they may experience depression and frustration with outcome. Patients in this study would by definition have failed to experience significant relief of parkinsonism despite best medical therapy. Alternatives to treatment in this study would include no additional treatment or other surgery, such as pallidotomy, thalamotomy, and subthalamotomy (significant additional risk for bilateral procedures).

The risks to subjects are reasonable in relation to the anticipated benefits to subjects as these patients have no predictably successful alternatives and would be expected to continue to decline functionally without treatment.

Patient-related data will remain confidential, with only numerical patient identification numbers being placed on data collection sheets. In the event of adverse effects to the subjects, patients would be cared for, including all appropriate specialty out-patient and in-patient care at Mayo Clinic in FL. Any unexpected or untoward outcomes encountered in this study would be reported to the IRB. Clinical data will be obtained both for research purpose and for clinical care as indicated. The medical record will be recorded in the Mayo Clinic electronic record. Data exclusive to this study will not be recorded in the Mayo Clinic electronic record but will be stored on paper record before being transcribed into electronic computer record form.

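### Benefit-risk is justified by a lack of alternatives, yet these patients would otherwise receive standard single-target DBS; what the fornix/hypothalamic lead adds in risk is not weighed

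*Combined protocol and SAP*

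**What the plan says.** The consent and risk paragraphs under Inclusion/Exclusion Criteria (Experimental Subjects) judge the risks reasonable on the ground that "these patients have no predictably successful alternatives and would be expected to continue to decline functionally without treatment". On the choices open to a candidate they state: "Alternatives to treatment in this study would include no additional treatment or other surgery, such as pallidotomy, thalamotomy, and subthalamotomy". Standard DBS at a motor target is not named.

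Other sections describe the same patients differently. The Description enrols people "who would otherwise be undergoing STN-DBS". Logistical Possibilities proposes to study patients "who are otherwise undergoing unilateral DBS-GPi or DBS-STN with a unilateral DBS electrode". The Summary that closes the background says DBS at the traditional motor targets "has provided improvement in functional “on” time and reduced tremor compared to standard medical therapy".

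On risk, the consent paragraphs list death, stroke, weakness on one side, visual field loss and the remaining hazards of stereotactic surgery, and add depression and frustration if expectations are not met. They give one rate: "The likelihood of such occurrences is generally reported to be approximately 2" per cent. They then report no such serious events in more than 100 procedures at the institution over two years. They also tie the surgical risks in the consent form to the list given there.

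The background section on whether DBS could affect cognition says: "Lesions in the fornix are also well known to produce memory deficits in humans".

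**The concern.** A benefit-risk judgement depends on its comparator. If the alternative is continued decline without treatment, the whole benefit of the motor lead counts in favour of the study and the whole operation is needed to obtain it. If the alternative is the single-target DBS the patient was going to have anyway, the motor lead drops out of the comparison. What remains is one more electrode in the same hemisphere, plus stimulation at a new target, against a cognitive gain that the study exists to explore.

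The consent paragraphs argue from the first comparator, while the rest of the protocol describes the second. So the protocol has not justified the risk that the research itself imposes. The risk list also leaves out worsening of cognition, the function measured by the primary endpoint, although the background gives reasons to consider it.

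**Working it through.** **1. The comparator.** Four statements, side by side:

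- Consent paragraphs: no predictably successful alternative; the options are no further treatment or lesion surgery.
- Description: without the study, the patient has STN-DBS.
- Logistical Possibilities: without the study, the patient has unilateral GPi- or STN-DBS.
- Background Summary: such DBS improves functional on time and tremor relative to medical therapy.

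The first cannot stand with the other three as a statement about motor disability. The consent paragraphs are about motor disability: just before the alternatives they describe the patients as people whose parkinsonism was not adequately relieved by medication.

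**2. The increment.** Logistical Possibilities requires at least two electrodes in one hemisphere. Surgical Technique places the hypothalamic electrode directly after the motor electrode, in the same operation. The research component is therefore the second lead and its stimulation. No section gives a risk for it.

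**3. The stated rate.** The 2% is quoted as generally reported, without derivation, so there is nothing to reproduce. It is not said to be per lead, per operation or per patient. Inputs for the local record: 0 events, and n = 100 as the smallest count consistent with the text (more than 100).

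- Chance of no events in 100 if the true rate is 2%: 0.98^100 = 0.133, or 13.3%.
- One-sided 95% upper limit: 1 − 0.05^(1/100) = 2.95%.
- Two-sided 95% upper limit: 1 − 0.025^(1/100) = 3.62%.

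Both limits fall slightly if the count is larger. The record is compatible with 2% and also with a somewhat higher rate. The text does not say whether any of these procedures used two leads in one hemisphere or a fornix/hypothalamic lead.

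**4. How much the missing unit matters (illustration only).** The chance of at least one event in 12 patients is 1 − (1 − p)^12, where p is the per-patient risk.

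- p = 2% (the rate covers the whole operation and the second lead adds nothing): 21.5%.
- p = 3% (assumed): 30.6%.
- p = 1 − 0.98^2 = 3.96% (2% per lead, leads independent; both assumed): 38.4%.

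The 21.5% would apply equally to 12 patients having standard DBS at 2%, so it does not measure research risk. Only the gap between the lines does, and that gap is assumption.

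**5. Cognitive harm.** The background supplies these pieces:

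- Human fornix lesions cause memory deficits.
- High-current anterior thalamic DBS impaired memory in rats.
- Fornix/hypothalamic stimulation in one patient was followed by better memory performance.
- In the six-patient Alzheimer's series, 4 of 6 improved on the ADAS-Cog at 6 months, but at 12 months 5 of 6 scored higher (worse) than baseline, only one by more than expected. The protocol mentions no control group.
- The opening background section says available treatments, surgery included, often aggravate balance and cognitive problems in the short term.
- The Abstract concedes possible negative consequences of the new targets without naming any.

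This does not establish harm, but it leaves harm open, and the risk list is silent on it.

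**The case against.** The strongest defence is that the disputed sentence refers to cognition. Scientific basis or justification says existing surgery has some benefit but no influence on cognitive dysfunction, and neuropsychological scores are the primary endpoint. Read that way, the sentence is defensible. But the paragraph in which it stands speaks of unrelieved parkinsonism, so the contradiction remains until the wording is limited. The list of other surgery is open-ended, and the catch-all for stereotactic risks would cover a second tract in general terms. Neither names standard DBS, the increment over it, or effects of stimulation.

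A reader might also infer four stronger things, which the documents do not support:

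- *That the two-lead risk is about 4%.* This needs 2% per lead and independence between leads. Neither is stated. Both leads share one operation and one generator, and mapping may use one to five microelectrodes, so lead count is a poor proxy for risk.
- *That the local record excludes the fornix target.* The type of procedure is not stated, so this is unknown. Nor does the protocol claim that its record shows a risk below 2%.
- *That patients are not told they could have the same motor benefit without the second lead.* The consent form was not available. The protocol ties the form to its list of risks but does not say the same of alternatives. No section compares motor benefit with and without the second lead, and these patients were already expecting standard DBS.
- *That memory loss is a known harm of fornix stimulation.* The evidence is indirect, from lesions and from another target in rats, and the same section reports improvement with fornix/hypothalamic stimulation.

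**Conclusion.** The point holds as a contradiction within the protocol. The benefit-risk conclusion uses a comparator that the Description, Logistical Possibilities and background Summary rule out, at least for motor disability. This rests on the text alone, with no numerical assumption, and it has to be resolved because the conclusion on acceptable risk depends on it.

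Two further gaps follow. First, the rate of about 2% and the local record cannot be applied to a two-lead procedure as written; taken at 100 procedures, zero events leaves an upper 95% limit of about 3.0% one-sided or 3.6% two-sided. Second, possible cognitive worsening is absent from a list that is meant to feed the consent form.

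The size of the added risk cannot be derived from the documents. The figures of 4% per patient and 38% for at least one event in 12 are illustrations under assumptions the documents do not support, and they should not be read as estimates. What patients are actually told cannot be judged without the consent form.

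**What to change.** In the consent and risk paragraphs under Inclusion/Exclusion Criteria:

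1. Name standard STN- or GPi-DBS alone as an alternative.
2. Reconcile the sentence on alternatives with the Description, Logistical Possibilities and background Summary. If it is kept, limit it to cognition. Restate the justification as the risk that the fornix/hypothalamic lead and its stimulation add to standard DBS, weighed against an unproven cognitive benefit.
3. State whether the rate of about 2% is per lead, per operation or per patient. State whether the local procedures included two-lead or fornix/hypothalamic implants, and give the exact count with its upper limit. Insert no two-lead risk figure, because the documents supply none.
4. Add possible memory or cognitive worsening, and stimulation effects at the fornix/hypothalamic target, to the risks. Say that the evidence is indirect and that improvement has also been reported.
5. Check the consent form against the corrected text.

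The cost is protocol wording and a check of the form. No endpoint, visit or analysis changes. The downside is that the stated balance will look less favourable and some candidates may decline.
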